## **9. Safety Analysis**

The Safety Population and the Per-Protocol Safety Population will be used for the safety data summaries and analysis. All safety data collected will be listed. The safety and tolerability data summaries will be presented separately for the Safety Population and the PP Safety Population and will also be presented by BID and TID TPOXX/matching placebo dosing regimen. Safety will be assessed on the basis of AE reports, clinical laboratory data, vital signs, ECG parameters and physical examinations.

For all subjects that discontinued, data will be summarized by treatment group and dosing regimen, and reason for discontinuation.

### **9.1. Extent of Exposure**

All derived exposure variables and variables recorded on the eCRF will be listed by subject number.

### **9.2. Treatment Compliance**

Compliance will be derived for each subject and listed with exposure data.

% Compliance= (Number of capsules dispensed- Sum of number of capsules returned and lost) / (Number of capsules dispensed)X 100

Percentage compliance will be summarized by treatment group and dosing regimen using statistics for continuous variables, and the number of percentages of subjects achieving at least 92% compliance will be summarized by treatment group and dosing regimen.

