### **5.5.1 Subject Diary**

Clinical investigative sites will provide subjects with a subject diary and instructions on its completion. On days when study drug dosing does not occur at the clinical investigative site, subjects will be required to record the following information in their subject diary: the date and time they completed their meals (or the last time they ate), whether or not the meal they ate was the required meal of approximately 600 calories and 25 g of fat, the date and time of their study drug doses, whether or not they took 3 capsules of study drug at dosing, and a comments for any missed capsules or dose. Subjects will also enter into the diary any new or changed concomitant medications (including over-the-counter medications taken, such as vitamin, supplemental, and herbal preparations), with the start and stop date of the medication, the reason for use, and any symptoms or problems (illness or injuries) that subjects may have experienced.

Subjects will be instructed to record all AEs in the subject diary. Instructions will be provided by the clinical investigative sites advising subjects to record the start and stop dates that they experience AEs. Subjects will be instructed to bring the subject diary with them to all study visits. The subject diary will be reviewed by study site personnel with the subject at study visits.

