### **7.2            ANALYSIS SETS**

All populations will be identified and finalized before the database lock. All subjects who are randomly assigned are considered study subjects. Study populations are defined as the following:

- The Intent-to-Treat (ITT) Population will include all subjects who were randomly assigned to the study (i.e., a randomization number and randomization date are present in the database).

- The Safety Population will include all subjects who received at least 1 dose of TPOXX or matching placebo.
- The Per-Protocol (PP) Safety Population will include all subjects who received at least 92% of the doses of TPOXX or matching placebo 600 mg BID or TID dosing regimen over the 28 day treatment period.
- The PK Population will include all subjects in the PK subset who have taken at least 92% of the doses of the 600 mg BID or TID dosing regimen of TPOXX, have sufficient drug concentrations in plasma, and have no protocol deviations or other circumstances that would exclude the subject from analysis.

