### **4.6.3 Per-Protocol Safety Population**

The Per-Protocol (PP) Safety Population will include all subjects who received at least 92% of the 600 mg BID or TID dosing regimen of TPOXX or matching placebo.

If a subject takes less than 92% of study drug, then they will be considered ‘Course Too Short’ but will be included in the safety analysis.

The Per-Protocol Safety Population will also be used for all summary and analyses of safety endpoints.

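### SAP 9.2 scores capsules neither returned nor recorded as lost as taken, so a subject who stops early and keeps drug can score 100% and could wrongly meet the 92% rule

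*Combined protocol and SAP*

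**What the plan says.** SAP Section 9.2 gives one formula: "Compliance= (Number of capsules dispensed- Sum of number of capsules returned and lost) / (Number of capsules dispensed)X 100". It then reports how many "subjects achieving at least 92% compliance will be summarized by treatment group and dosing regimen". The only amount subtracted is the "Sum of number of capsules returned and lost", and the section does not define a lost capsule. It has no rule for bottles that never come back or for a missing return count, and it does not use any dosing record.

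The same 92% cut defines the Per-Protocol (PP) Safety Population. SAP Section 4.6.3 takes "all subjects who received at least 92% of the 600 mg BID or TID dosing regimen of TPOXX or matching placebo" and labels anyone who takes less as having had too short a course. Protocol Section 7.2 words the set in terms of doses received. SAP Section 4.2 sets the exposure goal of at least 300 TPOXX subjects at or above 92% of doses. Neither the PP definition nor the goal refers to the Section 9.2 formula.

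The protocol collects dose-level data separately. Section 5.5 puts the date and time of dosing, and the reason for a missed dose, into the eCRF. In the diary (Section 5.5.1), subjects record for each home dose "whether or not they took 3 capsules of study drug at dosing". Section 5.2.2 has all bottles, including empty ones, brought to every visit and inventoried.

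**The concern.** A returned-capsule count measures intake only if every capsule not taken comes back or is declared lost. When that fails, the formula errs in one direction: missing capsules become taken capsules.

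The design leaves room for this. For subjects outside the PK subset, Protocol Table 9-2 shows drug dispensed once, after the Day 1 dose, and collected once, at Day 29 or early termination. All doses after the first are taken unobserved at home. Protocol Section 4.4.2 foresees subjects who do not return for final assessments, but says nothing about their capsules.

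The compliance table is directly exposed. Membership of the PP Safety Population and the count toward 300 are exposed if Section 9.2 is the variable behind the 92%. An early dropout wrongly placed in the PP set would sit in the denominator of its AE rate as a fully exposed subject and, unless an AE had already been reported, as AE-free. That tends to lower the PP AE rate.

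**Working it through.** **The plan's own figure.** SAP Section 4.2 states about a 95% chance of seeing at least one AE of 1% incidence in 300 subjects. 1 − 0.99^300 = 0.9510, so the figure reproduces.

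**Inputs.**
- Supply (Protocol 5.2.1): 4 × 42 = 168 capsules for BID, 6 × 42 = 252 for TID.
- Planned doses (SAP 4.4): 56 or 84, at 3 capsules each. 56 × 3 = 168 and 84 × 3 = 252, so the supply equals the regimen with no overage.
- TPOXX arm: 445 × 4/5 = 356. The goal of 300 leaves 356 − 300 = 56 subjects of slack.

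**What 92% allows.** 0.92 × 56 = 51.52, so at least 52 doses are needed and 4 may be missed. 0.92 × 84 = 77.28, so at least 78 are needed and 6 may be missed. In capsules, 0.92 × 168 = 154.56 (155 needed, 13 may go untaken) and 0.92 × 252 = 231.84 (232 needed, 20 may go untaken). One full bottle of 42 exceeds either allowance, so how one bottle is recorded can decide a subject's classification.

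**A subject who keeps the whole supply.**
- Entered as 0 returned, 0 lost: (168 − 0)/168 = 100%; (252 − 0)/252 = 100%.
- All capsules entered as lost: (168 − 168)/168 = 0%; (252 − 252)/252 = 0%.
- Return count missing: no value.

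With 0 returned and 0 lost, the score does not depend on when dosing stopped:

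| Last dose taken | Doses taken / planned | SAP 9.2, 0 returned and 0 lost | SAP 9.2, unused capsules returned |
|---|---|---|---|
| Day 1 clinic dose only | 1/56 = 1.8% (BID), 1/84 = 1.2% (TID) | 100% | 1.8%, 1.2% |
| End of Day 7 | 25% | 100% | 25% |
| End of Day 14 | 50% | 100% | 50% |
| End of Day 21 | 75% | 100% | 75% |

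The formula is right when unused drug is returned and wrong when it is neither returned nor recorded as lost.

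**A subject who leaves one bottle at home.** A BID subject who stops after Day 21 has taken 21 × 2 × 3 = 126 capsules, and 168 − 126 = 42 remain, exactly one bottle. If the three empty bottles come back and the full one does not, the score is (168 − 0)/168 = 100% against a true 126/168 = 75%. If that bottle is entered as lost, the score is (168 − 42)/168 = 75%. The record of one bottle moves the subject across the 92% line.

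**Effect on the detection statement.** Let k of the 300 counted subjects be misclassified in this way; k is an assumption. Then 1 − 0.99^(300 − k) is:
- k = 0: 95.1%
- k = 5: 94.8%
- k = 10: 94.6%
- k = 20: 94.0%
- k = 30: 93.4%

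**The case against.** The strongest reply is that the populations rest on doses received or taken, not on the Section 9.2 formula. On that wording, a subject who vanishes in the first week has not received 92% of 56 doses and is out. This stands in part. A reader might infer that the plan places such a subject in the PP set and the 300 count, but no text says so. Still, Section 9.2 is the only derivation offered and uses the same cut. If another record is meant, the SAP does not name it.

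Second, a reader might infer that a subject who disappears with the bottles always scores 100%. The documents do not support that: the result may be 100%, 0% or missing, depending on an entry convention that is not stated.

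Third, other records would expose an early dropout: the inventory at each visit, the eCRF dosing entries, the disposition table (SAP 5.1) and the administration listings (SAP 7.3). Populations are also finalised before database lock. All of this makes the case visible, but none of it overrides the formula.

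Fourth, the PK Population is largely protected. SAP Section 4.6.4 requires sufficient concentrations and no excluding deviations, with case-by-case review by the pharmacokineticist. That stands.

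Finally, diaries are self-reported, and a subject who keeps the bottles may keep the diary too. That is a real limit on a diary-based measure. However, an undocumented dose would then count as not taken, which avoids crediting exposure for which there is no record.

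**Conclusion.** The formula as written can give a wrong value: it credits as taken every capsule neither returned nor recorded as lost. This directly affects the compliance summary. It could also affect membership of the PP Safety Population and the 300-subject count, on the inference that Section 9.2 supplies the 92%.

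The number of subjects affected is unknown. It is tempting to apply an assumed loss rate to the 356 TPOXX subjects and conclude that the goal of 300 could be reported as met when it was not. The documents give no such rate, so that conclusion is not supported. On the detection probability the effect is small: about one percentage point at an assumed 20 misclassified subjects. The Safety Population requires only one dose, so its AE analysis does not change. SAP Section 9.3 also plans the AE comparison in the PP set, but the SAP's table index lists that comparison for the Safety Population only.

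The main harm is possible wrong membership of the PP set, with early dropouts treated as fully exposed. The change is worth making before the populations are finalised.

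**What to change.** In SAP Section 9.2:
- Define compliance as documented doses (site-observed doses plus eCRF- or diary-recorded doses of 3 capsules) divided by planned doses, 56 or 84.
- Keep the capsule count as a cross-check.
- Define a lost capsule, and do not count unreturned capsules without a dosing record as taken.
- State that this variable determines the 92% rule for the PP Safety Population, for the PK Population built on it, and for the 300-subject count.
- Where bottles came back but diary pages are missing, use the capsule count.

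Under this rule, subjects who vanish after Day 7, 14 or 21 score at most 25%, 50% or 75%, and all fall outside the PP set.

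The cost is SAP wording, since the dosing records are already collected. The downside is that missing diary pages will lower some compliance values. The documents do not allow an estimate of how many; the capsule-count fallback limits this where bottles were returned.

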### **9.3. Adverse Events**

The primary objective of this study is to determine the safety and tolerability of TPOXX when administered orally for 28 days in adult subjects. The overall AE rate in the Safety Population and the Per-Protocol Safety Population will be compared between treatment groups using a stratified Mantel-Haenszel test accounting for age (18 to 30 years, 31 to 45 years, 46 to 64 years, and 65 to 80 years). If expected cell counts are less than 5, then Fisher's exact test will be applied. The AE rate is the number of subjects who report at least 1 post-dose AE expressed as a proportion of the number of subjects in the Safety Population and the Per-Protocol Safety Population. An exact unadjusted 95% confidence interval (CI), calculated using the Clopper-Pearson method, will be given for each treatment group. For the difference in AE rates between the treatment groups, a continually corrected exact 95% CI around the difference will be calculated. In addition, the Mantel-Haenszel adjusted odds ratio and 95% Cis from the stratified analysis will be presented.

#### **9.3.1 Time to First Adverse Event**

Time to first AE is defined as the duration from start of the treatment to the first recorded post-dose AE. If the subject does not have an AE, time to first event will be censored at the date of the last adequate assessment; this is expected to be on the Day 42 (+2 day) Follow-up Telephone Call.

Time to First AE (days) = (Date of first AE – Date of first dose) +1

Time to first AE will be analyzed using Kaplan Meier (KM) quartile estimates along with 2 sided 95% CIs. Treatment groups will be compared using the log rank test stratified by age group and clinical investigative site. Statistical significance will be assessed at the 0.5 level. A summary table will be produced.

If a subject does not experience any AE during the study, the time to first AE will be censored at the date of study completion.

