## **7.            STATISTICAL ANALYSIS PLANS**

### **7.1            SAMPLE SIZE CALCULATIONS**

There is no formal sample size calculation for this study. Although the sample size is not based on statistical power considerations, administration of TPOXX 600 mg to 300 subjects provides approximately 95% probability of observing at least 1 occurrence of any AE if the incidence of AEs in the study population is 1% and is considered adequate to provide a reasonable assessment of safety and tolerability. A sufficient number of subjects will be randomly assigned to ensure that at least 300 subjects receive at least 92% of the doses of the BID or TID dosing regimen of oral TPOXX 600 mg over the 28-day treatment period.

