Time from the first dose to the first AE or to discontinuation from study for any reason will be analyzed using Kaplan-Meier quartile estimates along with 2-sided 95% CIs. Treatment groups will be compared using the log rank test stratified by age group and site. If a subject does not experience any AE or does not discontinue from study, the time to first AE or time to discontinuation will be censored at the date of study completion.

Toxicity grades for laboratory tests will be determined according to the DAIDS AE Grading Table. The maximum postbaseline grade increase from baseline grade will be summarized by treatment group and BID and TID study drug dosing regimen and overall for the Safety Population and PP Safety Population using frequency and percentage of subjects with increase to grade 1, 2, 3, 4, 1 to 4, 2 to 4, and 3 to 4, respectively.

Actual values and changes from baseline for clinical laboratory test results, vital sign measurements, and 12-lead ECG results will be summarized by treatment group and BID and TID study drug dosing regimen at each time point using descriptive statistics (number of subjects, mean, SD, median, minimum, and maximum). Shift tables will be generated for clinical laboratory test results. Physical examination findings will be presented in a data listing.

Narratives will be presented for all deaths, subjects who reported SAEs, subjects withdrawn because of AEs, and grade 3 AEs deemed by the investigator to be possibly, probably, or definitely related to study drug.

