## **3. Study Design and Description**

This is a Phase 3, multicenter, double-blind, randomized, placebo-controlled study to assess the safety, tolerability, and PK of oral TPOXX 600 mg when administered for 28 days in adult subjects.

A total of at least 445 subjects (includes a PK subset of 40 subjects), ages 18 to 80, inclusive, will be enrolled and randomly assigned within stratified age groups (18 to 30 years, 31 to 45 years, 46 to 64 years, and 65 to 80 years) to 1 of 2 treatment groups in an overall randomization of 4:1 (approximately 356 subjects will receive TPOXX and 89 subjects will receive TPOXX matching placebo). There will be 2 dosing regimens based on the subject's body weight: subjects with a body weight of 120 kg or less will be administered either TPOXX 600 mg or placebo two times a day (BID), 12 hours apart ( $\pm$ 30 minutes); and subjects with a body weight of more than 120 kg will be administered TPOXX 600 mg or placebo three times a day (TID), 8 hours apart ( $\pm$ 30 minutes). The study will consist of a screening period (Day -28 to Day -2), 1 check-in, on-site visits (Day 7, Day 14, and Day 21), a dosing complete/ET visit (Day 29), and 2 follow-up telephone calls (Day 42 [+2 days] and Day 58 [+2 days]). The total duration of the study for each subject, including screening, treatment, and follow-up telephone calls will be approximately 86 days,

The enrollment goal for the study is to randomly assign a sufficient number of subjects to ensure that at least 300 subjects receive at least 92% of the oral TPOXX 600 mg BID or TID dosing regimen over the 28-day treatment period. Overall, across all clinical investigative sites, a goal of approximately 20% of subjects (i.e., 89 subjects) or more will be enrolled and randomly assigned in each age group to ensure a representative investigation of TPOXX safety and PK across age groups. The treatment groups will be as follows:

- Treatment Group 1: An oral dose of 600 mg (3 × 200-mg capsules) TPOXX BID (every 12 hours [ $\pm$ 30 minutes]) for subjects with a body weight of 120 kg or less or TID (every 8 hours [ $\pm$ 30 minutes]) for subjects with a body weight more than 120 kg for 28 days (Day 1 to Day 28).

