## **4.5. Endpoints**

### **4.5.1 Safety Endpoints**

The primary outcome measure is the evaluation of the safety and tolerability of twice or three times daily oral dosing of TPOXX 600 mg for 28 days through adverse event (AE) findings, clinical laboratory tests, vital sign measurements, electrocardiogram (ECG) tests, and physical examinations. The primary endpoint is the AE rate. Other endpoints include severe AE rate, time to first AE and time to withdrawal for any reason.

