### **9.3.2 Time to Withdrawal for Any Reason**

Time to Withdrawal for Any Reason is defined as the duration from start of treatment to study withdrawal for any reason. If the subject does not discontinue from the study, time to withdrawal for any reason will be censored at the date of study completion; this is expected to be the Day 42 (+ 2 days) Follow-up Telephone Call.

Time to Withdrawal for Any Reason (days) = (Date of study withdrawal – Date of first dose) + 1

Time to Withdrawal for Any Reason will be analyzed as described above for the time to first AE.

If a subject does not discontinue or withdraw from the study, the time to discontinuation will be censored at the date of study completion.

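### Time to withdrawal is estimated only by Kaplan-Meier quartiles, which are unlikely to be reached at the planned 356/89, so the endpoint would probably yield a log-rank p-value without a time-to-event estimate

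*Combined protocol and SAP*

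**What the plan says.** SAP 4.5.1 makes the AE rate the primary endpoint and adds: "Other endpoints include severe AE rate, time to first AE and time to withdrawal for any reason". For time to first AE, SAP 9.3.1 states: "Time to first AE will be analyzed using Kaplan Meier (KM) quartile estimates along with 2 sided 95% CIs". The comparison is: "Treatment groups will be compared using the log rank test stratified by age group and clinical investigative site". SAP 9.3.2 carries both over: "Time to Withdrawal for Any Reason will be analyzed as described above for the time to first AE". Protocol 7.3.2 likewise says that the two times "will be analyzed using Kaplan-Meier quartile estimates along with 2-sided 95% CIs".

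Neither document asks for a Kaplan-Meier probability at a fixed day, a hazard ratio or a Kaplan-Meier curve. SAP 9.3.1 promises a summary table, but the index in SAP Section 14 lists no time-to-event table or figure.

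On size, SAP Section 3 plans that "approximately 356 subjects will receive TPOXX and 89 subjects will receive TPOXX matching placebo", within a total of at least 445. Protocol 7.1 aims for "at least 300 subjects receive at least 92% of the doses of the BID or TID dosing regimen of oral TPOXX 600 mg". SAP 9.3.2 censors subjects who do not withdraw at study completion, which it expects to be the Day 42 (+2) call. SAP 4.6.3 and Section 9 repeat the safety analyses in the PP Safety Population.

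**The concern.** A Kaplan-Meier quartile is a time, and it exists only once the curve has fallen far enough: to 75% event-free for the 25th percentile, 50% for the median and 25% for the 75th percentile. When events are uncommon the curve never gets there and the table reads 'not reached'. Early withdrawal from a 28-day study in generally healthy adults may well be uncommon, and the dosing target suggests a level well below a quarter of the TPOXX arm at the planned size.

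Time to withdrawal is one of the named measures of tolerability, and tolerability is part of the primary objective. If the quartiles are not reached, the specified analysis leaves only a test result. A reader would have no estimate of how much withdrawal differs between arms or how precisely that is known.

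**Working it through.** **Inputs.** 356 TPOXX and 89 placebo (SAP Section 3); at least 300 TPOXX subjects with at least 92% of doses (Protocol 7.1); 56 doses BID or 84 TID over 28 days (SAP 4.4); censoring at about Day 42 (SAP 9.3.2). No withdrawal rate and no overall AE rate is given, so those are varied.

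**The plan's own figure.** The probability of at least one AE in 300 subjects at 1% incidence is 1 − 0.99^300 = 0.951, which matches the stated 95%. The split also checks: 445 × 0.8 = 356 and 445 × 0.2 = 89.

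**What the dosing target implies.** 300/356 = 84.3%, so at most 56 TPOXX subjects (15.7%) fall short if the target is just met with 356. 92% of doses is 51.52 of 56, so 52, or 77.28 of 84, so 78. On schedule, both are reached at Day 26 (52/2 and 78/3). A subject who meets the target has therefore stayed on drug to about Day 26, but may still withdraw afterwards.

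**Withdrawals needed per quartile** (no early censoring; q × n rounded up):

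| Quartile | TPOXX (356) | Placebo (89) |
|---|---|---|
| 25th | 89 | 23 |
| 50th | 178 | 45 |
| 75th | 267 | 67 |

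If all 56 who fall short withdrew, a further 89 − 56 = 33 TPOXX subjects would have to leave after about Day 26.

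**Chance of reaching the 25th percentile**, from the binomial tails P(X ≥ 89 | 356, p) and P(X ≥ 23 | 89, p):

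| True withdrawal rate p | TPOXX | Placebo |
|---|---|---|
| 5% | about 0 | about 0 |
| 10% | about 0 | 0.00002 |
| 15.7% | 0.000004 | 0.009 |
| 20% | 0.012 | 0.109 |
| 25% | 0.52 | 0.47 |

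**PP Safety Population.** Members took at least 92% of doses, so on schedule they did not withdraw before about Day 26. Only late withdrawals can count, and reaching 25% there is close to impossible in either arm, whatever the total enrolled.

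**Confidence limits.** With log-log limits, a lower 95% limit for the 25th percentile first appears at about 73 of 356 or 14 of 89 withdrawals. At a true 15.7%, P(X ≥ 14 of 89) = 0.54 on placebo; at 10% it is 0.06.

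**Time to first AE, at assumed AE rates.** The 25th percentile is reached with probability 0.012 on TPOXX and 0.109 on placebo at a 20% rate, 0.98 and 0.83 at 30%, and about 1.00 and 0.998 at 40%. At 40% the median is reached with probability about 0.0001 and 0.03.

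**What fixed-day probabilities would give.** At a 10% withdrawal risk, 1.96 × √(0.10 × 0.90/n) is 3.1 points on TPOXX and 6.2 on placebo. For the difference, √(3.1² + 6.2²) is about 7.0 points (unrounded inputs). At 15.7% observed, 56/356 has an exact 95% CI of 12.1% to 19.9%, and 14/89 has 8.9% to 25.0%.

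**The case against.** The strongest reply is that the 300-subject figure is not a retention target. It counts TPOXX subjects by doses taken, and it can be met by randomizing more subjects or by replacing those who withdraw (Protocol 4.4.4). With 400 on TPOXX (500 in total), 300 compliant subjects leave exactly 25% non-compliant. It sets nothing for placebo and does not limit withdrawal after about Day 26. All of this stands. A reader might infer that the plan's own target makes the quartiles non-estimable; it makes them unlikely at the planned size, under an assumed rate.

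A reader might also infer that every quartile and every confidence limit would be blank in both arms. That goes too far: at 15.7% a lower limit on placebo is slightly more likely than not. Nor does the same failure follow for time to first AE. The dosing target says nothing about AE incidence, the 1% in the sample-size text only illustrates detection of an event, and the 25th percentile is likely to be reached once the AE rate is clearly above 25%.

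Finally, the trial is not left without withdrawal or AE estimates. SAP 5.1 gives numbers and percentages discontinued, with reasons, by treatment, and with near-complete follow-up the final Kaplan-Meier value would be close to that percentage. SAP 9.3 gives AE rates, their difference and an odds ratio with CIs. A 'not reached' entry also tells the reader that withdrawal stayed below 25%. What these outputs lack for withdrawal is a confidence interval, a between-arm difference and any timing.

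**Conclusion.** The point holds for time to withdrawal. At 356/89, and with true withdrawal at or below about 15.7%, the 25th percentile would almost surely not be reached on TPOXX (0.000004) and very probably not on placebo (0.009); the median and 75th percentile are further away. In the PP Safety Population this is close to certain by construction. The specified analysis would then very likely yield a log-rank p-value with no time-to-event point estimate and no between-arm difference.

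The 15.7% is an assumption taken from the dosing shortfall, since the documents state no withdrawal rate. The conclusion weakens at 20% (0.012 and 0.109) and fails near 25%. It also assumes little early censoring. This is one of the other endpoints; the primary AE-rate analysis is unaffected. The change is worth making because it is nearly free, not because the trial's main conclusion is at risk.

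**What to change.** In SAP 9.3.2, add the Kaplan-Meier cumulative probability of withdrawal by arm with 95% CI, and the between-arm difference with 95% CI, at Day 28 and at the end-of-study horizon. Settle that horizon first: SAP 9.3.2 expects completion and censoring at the Day 42 (+2) call, whereas Protocol Section 3 follows subjects to a Day 58 (+2) call and Protocol 9.3.3.3 counts the follow-up calls in the end of study. A Day 58 estimate would be meaningless if subjects are censored at Day 42.

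Keep the quartiles and report them where estimable. List the time-to-event output in SAP Section 14, and align Protocol 7.3.2 at its next amendment or record the addition in SAP Section 11. For time to first AE the same rows are optional.

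The cost is SAP wording and a few table rows from curves that are already to be fitted. No new data are needed.
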